8.1. Overview

We will conduct a Stage 1 pilot feasibility study at McLean Hospital to develop a combination of medication protocol to treat cannabis dependence in subjects with schizophrenia, schizoaffective, or any Axis I disorder. In a randomized, double-blind, placebo-controlled trial, 18 cannabis-dependent male an female subjects ages 18-45 with an Axis 1 psychiatric disorder will receive medical management (MM) over a 10-week period, with half receiving treatment with the combination of dronabinol and clonidine and half receiving placebo. Subjects will receive either the combination of dronabinol 5 mg by mouth three times daily and clonidine 0.1 mg my mouth twice daily or placebo in addition to MM over a 10-week treatment period. A follow-up visit after treatment at week 14 will evaluate the durability of treatment effects on drug use and psychosocial outcomes. Primary outcomes will include self-report of cannabis smoking and results of quantitative urine drug screens for cannabis. We also will assess cannabis withdrawal symptoms, including mood and craving. Mixed models ANOVA will be used to analyze the data.

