8.2. Participants

Subjects are cannabis-dependent male and female volunteers with mental illness ages 18-45 years old and will be recruited via newspaper advertisements, word of mouth, web-based advertisements, and the Psychotic Division Clinical Research Core (Protocol # 2009-P-002016)..

A total of 18 cannabis-dependent volunteers with (9 men, 9 women) an Axis 1 psychiatric Disorder will serve as subjects. Factoring in a potential 20% dropout of those who actually begin the protocol, we estimate that 7-8 people will probably be exposed to dronabinol in this pilot study. In order to meet the target sample of 18 completers (8 subjects per group), we expect to recruit about 50 subjects and have 35 sign the informed consent form. Of those who sign the informed consent form, 14-18 will probably end up being randomized.

Women must use a medically-approved method of contraception to participate in the study (e.g. birth control pills, IUD, condoms). During the physical, the physician will ensure that the potential volunteer is using adequate methods to prevent pregnancy.

Briefly describe study procedures. Include any local site restrictions, for example, "Subjects enrolled at McLean will not participate in the pharmacokinetic portion of the study." Describe study endpoints.

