Subjects will be instructed to keep us informed of any medications initiated after their enrollment in the study. Subjects will be reminded of the potential for additive CNS depression resulting from concomitant use of dronabinol and alcohol, opioid analgesics, benzodiazepines, and barbiturates. They will be warned initially of these potential additive effects during the informed consent process. Participants will be warned not to drive, operate machinery, or engage in any hazardous activity while receiving dronabinol. Subjects will also be informed that clonidine may cause drowsiness, dizziness, or lightheadedness associated with orthostatic hypotension. These effects may be worse if taken with alcohol or other medications that can cause drowsiness. Subjects will be warned not to abruptly stop taking clonidine.

Partners Human Subjects Research Application Form

Subjects will also be informed that data on the use of antipsychotic medications and dronabinol and/or clonidine is lacking. Due to the potential for sedation and possible hypotension in subjects taking these medications together, we will monitor carefully for these symptoms while educating subjects about these possible side effects.

- 8.2.1.b. Informed consent. Eligible subjects will complete standard consent documentation. Prior to the volunteer being asked any question about his/her health, the volunteer will be given a consent form to read. The research assistant will go over it in detail with the volunteer. After a physician investigator answers any questions the volunteer may have concerning the study, he/she will be asked to provide their informed consent to the licensed physician investigator. If enrolled in the study, consent to communicate with their other clinicians will be obtained. Clinicians will be notified of their patients' enrollment in the study, thus allowing them to carefully monitor for changes in mood while they are undergoing treatment to stop use of cannabis.
- 8.2.1.c. Randomization. Research staff will stratify subjects according to their self-reported frequency of cannabis use in the past 30 days: 1) daily use; and 2) non-daily use. The stratification procedure will guard against the possibility that one of the experimental conditions (i.e., dronabinol-clonidine or placebo) will be overrepresented by daily users, while non-daily users will predominantly be randomized into the other condition.

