8.5.2.a. Urine Screens. The primary outcome measure will be cannabis use, as measured by twice-weekly quantitative urine screens during treatment. Quantative urine screens will also be measured during weeks 11, 12, 13, and 14 following the 10-week treatment period. Cannabis is a particularly challenging drug of abuse for measuring outcome because of the false-positive urine screens that can occur as the result of long-term accumulation of cannabis metabolites. In an attempt to avoid false-positive results, we will obtain 2 supervised urine samples weekly: 1 at the medical visit and 1 on another day, ordinarily with 3-4 days separation from the clinical visits (e.g., Monday-Thursday, Tuesday-Friday, or Monday-Friday); this should maximize the time frame covered by our urine screens. We will send the urine samples to Quest Diagnostics Laboratory (Cambridge, MA, a NIDA-certified laboratory), where the urines

Partners Human Subjects Research Application Form Version Date: July 26, 2016

will be screened by immunoassay for the THC metabolite 11-nor-carboxy-∆ 9tetrahydrocannabinol (THC-COOH) as well as other drugs of abuse. Urine creatinine concentrations will also be measured to assess urine concentration. The threshold for detection of THC-COOH will be 20 ng/ml. Samples positive for this metabolite will undergo further analysis by gas chromatography-mass spectroscopy to obtain quantitative THC-COOH concentration; we will then calculate the ratio of this metabolite to urine creatinine concentration. We will adopt the method of Heustis and Cone (1998) to differentiate new marijuana use from residual drug excretion as a result of previous use; these recommendations are based on their controlled clinical studies of urinary excretion profiles of creatinine and marijuana metabolites following marijuana administration in humans. We will label a urine negative (i.e., abstinent from cannabis) if 1) the ratio of THC-COOH to creatinine in the urine does not increase by >50% from the ratio obtained in the previous urine screen, and 2) the subject also reports using no cannabis since the previous urine test.

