All data collected will be de-identified with subject ID numbers and used for research purposes only. Written records will be kept in a locked file cabinet in a locked office. They will be destroyed after 5 years. Computerized data files will also be de-identified with subject ID numbers and kept in a password protected file on a password protected computer.

8.9. Statistical Analysis

The primary data analysis will be an intent-to-treat analysis, which includes all randomized subjects. Of note, every attempt will be made to continue assessing subjects even if they drop out of treatment. In addition, we will replicate all analyses with the completers only. The primary and secondary outcome variables are intended to

Partners Human Subjects Research Application Form Version Date: July 26, 2016

explore various aspects of response to therapy and to help define a clinically meaningful response. The primary outcome measures, Actiwatch-scores, daily diaries, TLFB self-report data, in addition to quantitative urinary THC metabolites, have been chosen for their ability to indicate daily use of cannabis by relying on self-report of use.

Specifically, for assessing the effect of dronabinol and clonidine on cannabis use patterns, we propose to use the generalized estimating equations (GEE) approach to longitudinal analysis, appropriately accounting for the positive correlation among repeated urine screen assessments within the same individual.

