Analyses of secondary substance use outcomes will focus on the number of days of cannabis use and of any substance use (and conversely, days of abstinence) during treatment and post-treatment follow-up. In addition, we will also examine the ASI Drug and Alcohol composite scores. Frequency of days of cannabis use (and any substance use and days of abstinence) will be analyzed via a log-linear (or Poisson) regression model, controlling for pre-treatment frequency of days of cannabis use. Although loglinear regression methods are considered appropriate for the analysis of count or frequency data, in many biomedical applications, count data have variability that far exceeds that predicted by the Poisson distribution; we expect that days of cannabis use (and any substance use and days of abstinence) will not be an exception. Linear mixed effects models will be used to examine the effect of treatment group on changes in the ASI Drug and Alcohol composite scores during treatment and post-treatment follow-up assessments (as determined by the group-by-time interaction in the linear mixed effects regression models). The linear mixed effects model will include random intercepts and slopes to appropriately account for correlation among repeated measures and heterogeneity of variance over time; the model will be fit using PROC MIXED in SAS.

In secondary analyses of mood outcomes, mood episodes will be assessed during treatment and post-treatment follow-up, using the QIDS-SR, , BAI, and BIS-11; ; changes in risk of mood episodes during treatment and post-treatment follow-up assessments will be analyzed via a logistic regression model (similar to the logistic model above) that will be fit using the GEE approach (as implemented in PROC GENMOD in SAS) to account for correlation among repeated binary outcomes on the same individual. To examine the effect of dronabinol and clonidine on changes in risk for mood episodes during treatment and post-treatment follow-up, the logistic regression model will include the effects of treatment condition and the baseline measure of the outcome.

For studies involving treatment or diagnosis, provide information about standard of care at McLean (e.g., BWH, MGH) and indicate how the study procedures differ from standard care. Provide information on available alternative treatments, procedures, or methods of diagnosis.

The standard of care for cannabis dependence is psychotherapy; our treatment centers upon a medication.

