- 9.1. Sample Size: In order to meet the target sample of 18, We plan to screen 50 subjects ages 18-45 in the course of 20 months to achieve our desired sample size.
- 9.2. Advertising: Subjects will be recruited via websites, newspaper advertisements, flyers on campus, word-of-mouth, and the Psychotic Division Clinical Research Core. We will not specifically recruit subjects from particular patient units at McLean. Subjects may not be inpatients at McLean at the time of their participation in the study.

9.3. Inclusion criteria Inclusion:

1) Age range 18-45 years; 2) DSM-IV diagnosis of cannabis dependence, based on the Structured Clinical Interview for DSM-IV (SCID); 3) DSM-IV diagnosis of an Axis 1 psychiatric disorder, based on the Structured Clinical Interview for DSM-IV (SCID); 4) express a desire to quit cannabis use within the next 30 days; 4) have used cannabis on 20 days within the past 30 days (i.e., an average of 5 day per week); 5) identify cannabis as their primary drug of abuse; 6) stable on antipsychotic medication for 1 month; 7) for women of childbearing age, a negative pregnancy test at screening with agreement to use adequate contraception to prevent pregnancy and monthly pregnancy tests; 8) consent for us to communicate with their prescribing clinician if one exists; 9) furnish the names of 2 locators, who would assist study staff in locating them during the study period; 10) live close enough to McLean Hospital to attend study visits; 11) plan to stay in the Boston area for the next 3 months; 12) are willing and able to sign informed consent; and 13) must be psychiatrically stable, with no psychiatric medication changes in the 4 weeks prior to their screening visit.

Partners Human Subjects Research Application Form

Version Date: July 26, 2016

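### The urine GEE in section 8.9 will rest on 14–18 subjects, but it names no small-sample-valid test and leaves out the daily/non-daily allocation stratum

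*Combined protocol and SAP*

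**What the plan says.** - **Numbers.** Section 8.2 sets a target of 18 and expects that "14-18 will probably end up being randomized". Half go to each arm (8.1), so 7–9 per arm. Section 8.9 makes the primary analysis intent-to-treat on all randomised subjects.
- **Outcome.** Section 8.5.2.a takes urine screens twice a week for 10 weeks, about 20 per subject. It defines a quantitative THC-COOH/creatinine ratio and also a binary label: "We will label a urine negative (i.e., abstinent from cannabis) if" two conditions on the ratio and on self-report hold.
- **Analysis.** Section 8.9 states "we propose to use the generalized estimating equations (GEE) approach to longitudinal analysis, appropriately accounting for the positive correlation among repeated urine screen assessments". It gives no link, model terms, working correlation, variance estimator, test, reference distribution or alpha. Section 9.1 on sample size does not supply them. Section 8.1 names a different method for the data, mixed models ANOVA.
- **Allocation.** Section 8.2.1.c says "Research staff will stratify subjects according to their self-reported frequency of cannabis use in the past 30 days", into daily and non-daily users. It gives no block size or other allocation method, and no model in 8.9 contains the stratum.
- **Secondary models, for contrast.** The count model is fitted "controlling for pre-treatment frequency of days of cannabis use". The mood outcome, with its baseline as a covariate, "will be analyzed via a logistic regression model (similar to the logistic model above) that will be fit using the GEE approach". No logistic model is written out before that point.

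**The concern.** The robust sandwich variance is justified as the number of independent subjects grows. Taking 20 urines from each subject does not help: with 7–9 subjects per arm the uncorrected variance is too small on average, and a normal reference adds to the problem. The plan leaves the choice of test to a software default or to whoever runs the analysis.

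The stratum matters for the same p-value. Leaving out a prognostic stratum that was balanced by design makes the standard error too large for the comparison; adding it without a small-sample correction makes the liberal error worse. The two choices therefore need to be fixed together, before unblinding. At stake is the calibration of the urine-screen p-value and interval for Aim 1.

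**Working it through.** **Inputs from the documents.** 14–18 randomised (8.2), 1:1 (8.1), about 20 urines per subject (8.5.2.a), 20% dropout (8.2). **Assumed, because the plan is silent:** two-sided 5%, the test, positivity rates, within-subject correlation (ICC), the share of daily users, and how prognostic the stratum is.

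**1. The plan's own figures.** There is no alpha, power, effect size or variance, so no calculation can be reproduced. The counts give 18/2 = 9 and 14/2 = 7 per arm, and 18 × 0.80 = 14.4 is near the low end of 14–18.

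**2. Quantitative outcome, non-prognostic stratum, uncorrected robust Wald z.** With n subjects per arm and within-arm sums of squares SS₁ and SS₀, the sandwich variance of the difference is (SS₁ + SS₀)/n². The pooled t test uses (SS₁ + SS₀)/[n(n − 1)]. Rejecting at |z| > 1.96 is therefore the same as |t| > 1.96·√((n − 1)/n) on 2n − 2 degrees of freedom.
- n = 9: 1.96·√(8/9) = 1.848; P(|t₁₆| > 1.848) = 8.3%.
- n = 7: 1.96·√(6/7) = 1.815; P(|t₁₂| > 1.815) = 9.5%.

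**3. Binary urines, same test, by simulation** (beta-binomial subjects, 20 urines, no dropout or stratum effect). With 50–90% positive and ICC 0.3–0.7, the error was 6.1–14.6% (9 per arm) and 6.9–14.2% (7 per arm), about 6–15% overall. A separate simulation at 20–50% positive and ICC 0.3–0.5 gave 6.9–10.9% (N = 18), 7.6–13.3% (N = 14) and 4.9–5.6% at N = 100. The inflation is thus a small-sample effect.

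**4. Leaving out the stratum** (quantitative outcome, uncorrected Wald z, simulated):

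| Between-subject variance explained by stratum | Blocked within stratum, N = 18 / 14 | Unrestricted within stratum, N = 18 / 14 |
|---|---|---|
| 10% | about 7% / 8% | 8.8–9.2% / 10.6–11.0% |
| 25% | about 5% / 6% | same range |
| 40% | about 3% / 4% | same range |

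The offset appears only when allocation within strata is restricted.

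**5. Adding the stratum without a correction** (logistic GEE, balanced within strata, 800 trials per cell, simulation error about 1 point). With a prognostic stratum, the error was 12.6% (N = 14) and 10.0% (N = 18), against 6.4% and 4.8% when it was left out.

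**6. Other tests.**
- Robust score test, quantitative outcome: z² = [n/(n − 1)]·t² / [1 + t²/(2(n − 1))]. Setting z = 1.96 gives t = 2.084 (n = 9) and 2.130 (n = 7), so the error is 5.4% and 5.5%. For binary urines it was 1.7–5.8% and 1.1–5.9%, conservative near 90% positive.
- Mancl-DeRouen variance with a t reference: the standard error is multiplied by n/(n − 1), so the quantitative test rejects at |t| > t₀.₉₇₅·√(n/(n − 1)). For n = 9 this is 2.120·√(9/8) = 2.248, error 3.9%; for n = 7, 2.179·√(7/6) = 2.353, error 3.6%. For binary urines without the stratum, simulated error was about 2–8%, highest when most urines are positive.
- t test on subject proportions, 20–50% positive: 4.4–5.2% (N = 18) and 4.0–5.4% (N = 14).

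**7. Sparse stratum.** Section 9.3 requires subjects to "have used cannabis on 20 days within the past 30 days", so the non-daily stratum holds only frequent users and may be small. The binomial chance that a stratum has 2 or fewer subjects is 13.5% (N = 18) or 28.1% (N = 14) if 75% are daily users, and 48.0% or 64.8% if 85% are.

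**The case against.** The strongest reply is that the inflated rates belong to a test the plan never selects. That stands. A reader might infer that the planned analysis has a type I error well above 5%; the documents do not support this, because they name no test and a robust score test would be near 5% or below. The mixed models ANOVA of section 8.1 would not have these error rates either.

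A reader might also infer that leaving out the stratum safely cancels the inflation. The documents do not support that. Section 8.2.1.c aims to guard against imbalance, which suggests some restriction, but it states none, and step 4 shows no offset without one.

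Section 8.9 lists several primary measures (Actiwatch scores, diaries, timeline follow-back and urinary metabolites), so there is no single primary p-value to protect. This point concerns only the urine GEE. Finally, section 8.1 calls this a "Stage 1 pilot feasibility study", and 8.9 describes its outcomes as exploratory, with no power or confirmatory claim. That limits the consequences. It does not remove the gap: 8.9 still proposes a between-group assessment of treatment effect, and an interval from an uncorrected sandwich with a normal reference would usually be too narrow, even if p-values are only descriptive.

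**Conclusion.** The concern holds as a specification gap with modest stakes. Section 8.9 does not name a small-sample-valid test for a GEE on 14–18 subjects, and it omits the allocation stratum. If the usual uncorrected robust Wald z is used at an assumed two-sided 5%, the error is about 8.3–9.5% for a quantitative outcome with a non-prognostic stratum and about 6–15% for binary urines. The binary range rests on assumed positivity and correlation, and is not a probability statement about this trial. A prognostic stratum left out of the model would offset this only under restricted allocation within strata, which is not documented. It would go too far to call the analysis invalid, or to say that a re-randomisation test is required: such a test needs an allocation scheme that the documents do not give.

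**What to change.** In section 8.9:

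1. Reconcile the GEE with the mixed models ANOVA in 8.1. Say whether the GEE models the binary label or the quantitative ratio of 8.5.2.a; if binary, write out the logistic model to which the mood paragraph refers.
2. Report the treatment effect from the GEE with a bias-corrected sandwich variance (for example Mancl-DeRouen) and a t reference on subjects minus subject-level parameters, adjusted for the daily/non-daily stratum. Drop the stratum term if either stratum has fewer than 3 subjects, and do not add it without the correction.
3. If the logistic fit fails, compare subject-level proportions of positive urines by a t test, or by a within-stratum permutation test if the allocation scheme is recorded. State the denominator and how missed urines count.
4. State the alpha, or call the p-values descriptive. Apply the same correction to the mood GEE.

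**Cost.** Wording only, with no new data. Intervals widen: relative to the uncorrected z interval, the unadjusted quantitative case is (9/8)·(2.120/1.960) = 1.22 times as wide at 9 per arm and (7/6)·(2.179/1.960) = 1.30 times at 7 per arm. Some nominal power is lost, part of it only the removal of excess false positives. The correction is approximate, as the 2–8% in step 6 shows.

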8.5.2.c. Other Drug and Alcohol Use Assessment. Severity of cannabis and other substance use and its associated problems will be assessed at baseline and weeks 5,10, and 14 with the Addiction Severity Index (ASI, 5th edition) (McLellan et al. 1992), a widely-used and independently-validated interview that measures the severity of problems in 7 areas of functioning that are frequently affected in patients with SUDs: drug use, alcohol use, employment, legal status, medical condition, social functioning, and psychological status. In addition to our primary focus on marijuana use (urine screens plus days of use), we will examine other substance use (using urine screens plus days of other substance use). We will use this method to determine the number of days of marijuana use and of any substance use (and conversely, days of abstinence). We will examine ASI composite scores as secondary measures of substance use outcome. We will also use the self-administered Drug and Alcohol Use Questionnaire. This measure, administered at baseline, addresses the context of lifetime and recent drug and alcohol use, as well as sociodemographic data. At each treatment visit, patients will complete a brief Weekly Drug and Alcohol Use Inventory, indicating their number of days using marijuana, other drugs, and alcohol during the previous week. The Marijuana Goals Questionnaire (Griffin et al. 1989) is a brief guestionnaire administered at baseline to assess treatment goals, specifically, whether a subject is seeking abstinence or reduction in marijuana use. A 12-item self-administered questionnaire, the Marijuana Craving Questionnaire, will be used to assess craving at

Partners Human Subjects Research Application Form

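### Section 8.9 models days of any substance use, which can fall while alcohol or other drug use rises, and gives no model for the non-cannabis days that 8.5.2.c says will be examined

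*Combined protocol and SAP*

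**What the plan says.** Section 8.5.2.c (Other Drug and Alcohol Use Assessment) says that, beyond the main focus on marijuana, "we will examine other substance use (using urine screens plus days of other substance use"). It then describes deriving "the number of days of marijuana use and of any substance use (and conversely, days of abstinence"). At each treatment visit subjects complete the Weekly Drug and Alcohol Use Inventory, "indicating their number of days using marijuana, other drugs, and alcohol during the previous week". Table 1 also schedules this inventory at both baseline visits.

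Section 8.9 (Statistical Analysis) says the secondary substance use analyses "will focus on the number of days of cannabis use and of any substance use", with days of abstinence as the converse. The model is given in one sentence: "Frequency of days of cannabis use (and any substance use and days of abstinence) will be analyzed via a log-linear (or Poisson) regression model". The adjustment stated there, the same for all three counts, is "controlling for pre-treatment frequency of days of cannabis use". Section 8.9 adds that "we will also examine the ASI Drug and Alcohol composite scores", using linear mixed models with a group-by-time test. It names no model for days of non-cannabis use. For mood outcomes, by contrast, the same section includes the baseline value of the outcome itself as a covariate.

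Any substance use is not formally defined. Because its converse is abstinence, the ordinary reading is a day on which cannabis or any other substance was used.

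**The concern.** If cannabis use falls on active treatment, the natural next question is whether subjects moved to alcohol or other drugs. Section 8.5.2.c appears to plan for this, but the count modelled in 8.9 does not answer it. Entrants use cannabis on about two days in three, so cannabis days make up most of the any-substance count. A large fall in cannabis can therefore outweigh a rise in other use, and the count moves in the favourable direction.

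Substitution also bears on safety. The Safety Monitoring text in 8.2.1.a cites the dronabinol labelling on use with alcohol and other psychoactive substances, and the study restrictions warn of additive CNS depression.

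The covariate raises a second, smaller question. All the day counts are adjusted for pre-treatment cannabis days only, so a chance difference between groups in baseline alcohol or other drug use would go unadjusted in a trial of 18 subjects.

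**Working it through.** The plan gives no effect size, significance level or expected day count for this outcome, so there is no figure of its own to reproduce. The check asks when the any-substance count favours treatment although other use has doubled.

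**Inputs from the documents**
- Cannabis at entry (9.3): "have used cannabis on 20 days within the past 30 days", so c0 = 20/30 = 0.667 per day.
- Treatment period (8.1): 10 weeks = 70 days, so 0.667 × 70 = 46.7 cannabis days.
- Sample size (8.1): 18 subjects, 9 per group.

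**Assumptions**
- The control group stays at its entry rate.
- Treated cannabis use falls by 25%, 50% or 75%.
- The rate of other use, o, is not given; 5 to 25 of 70 days is tried.
- Other use doubles in the treated group.

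**Formula.** If cannabis and other use fall on days independently, any-substance days = 70 × [1 − (1 − c)(1 − o)]. With complete overlap the count is 70 × max(c, o). With no overlap it is 70 × (c + o).

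**Cannabis halved (46.7 to 23.3 days), other use doubled, independent days**

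| Other use, control → treated | Any-substance days, control → treated | Ratio |
|---|---|---|
| 5 → 10 | 48.3 → 30.0 | 0.62 |
| 10 → 20 | 50.0 → 36.7 | 0.73 |
| 15 → 30 | 51.7 → 43.3 | 0.84 |
| 20 → 40 | 53.3 → 50.0 | 0.94 |
| 25 → 50 | 55.0 → 56.7 | 1.03 |

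Second row written out: 70 × [1 − 0.333 × 0.857] = 50.0 and 70 × [1 − 0.667 × 0.714] = 36.7.

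**Break-even.** Setting the two groups equal gives o = (c0 − c1) / [2(1 − c1) − (1 − c0)].
- Cannabis halved: 0.333 / (1.333 − 0.333) = 0.333, or 23.3 of 70 days. Complete overlap (2o = c0) and no overlap (o = c0 − c1) give the same 23.3. In each case this is half the control group's cannabis days, so it would be lower if cannabis use also fell on placebo.
- Cannabis down 25% (c1 = 0.5): 0.167 / (1 − 0.333) = 0.25, or 17.5 days; 11.7 with no overlap and 23.3 with complete overlap.
- Cannabis down 75% (c1 = 0.167): 0.5 / (1.667 − 0.333) = 0.375, or 26.2 days; 23.3 with complete overlap. With no overlap, control other use cannot exceed 70 − 46.7 = 23.3 days, and the count favours treatment throughout that range.

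**Does comparing the two modelled counts reveal substitution?** With independent days, any-substance minus cannabis days equals 70 × o × (1 − c). Take other use of 10 days. In control the difference is 50.0 − 46.7 = 3.3. In the treated group with other use unchanged it is 10 × 0.667 = 6.7. With other use doubled it is 36.7 − 23.3 = 13.3. The difference doubles with no substitution at all, because there are more cannabis-free days on which other use is counted.

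**Does the covariate matter?** An over-dispersed Poisson model was fitted to simulated data with cannabis halved and other use rising from about 10 to 20 of 70 days. With 9 per group (1,000 runs) the median ratio for any-substance days was 0.73 whether adjusted for baseline cannabis days, for baseline any-substance days or for nothing. With 100 per group (100 runs) it was 0.74 in all three. Non-cannabis days in the same data, adjusted for their own baseline, gave a median ratio of 1.99.

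**The case against.** The strongest reply is that the plan is not blind to substitution. Section 8.9 models the ASI Alcohol composite separately, so a shift to alcohol has an outcome of its own. Section 8.2.1.a provides weekly urine toxicology and blood alcohol testing for the very reason that concurrent use is a hazard. Section 8.5.2.c already says that days of other use will be examined. A reader might infer that the trial cannot detect substitution at all; these provisions show that it can in part, and that objection stands. They do not close the gap, however. The ASI is a severity score planned at baseline and weeks 5, 10 and 14, not a day count. Its Drug composite is not stated to exclude cannabis. Section 8.9 specifies no between-group analysis of the toxicology and alcohol tests, and the statement in 8.5.2.c has no model attached.

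A reader might also infer that the any-substance result would be spurious. It would not. In the second row of the table, fully abstinent days rise from 70 − 50.0 = 20.0 to 70 − 36.7 = 33.3, a real gain on a legitimate outcome. It answers a different question.

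Nor does the baseline covariate produce the masking, as a reader might suppose: the simulated ratio is the same under every adjustment. In a randomised comparison the covariate affects precision and chance imbalance. Because cannabis days dominate the count, baseline cannabis days are not an unreasonable covariate for it, only an incomplete one.

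Finally, the rates of other use and its doubling are assumed. Section 9.4 excludes dependence on other drugs or alcohol, which makes lower rates plausible, but the documents give none.

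**Conclusion.** The point holds as a gap between the measures section and the analysis section. Section 8.5.2.c says that days of other substance use will be examined; 8.9 models cannabis days and a combined count that includes cannabis on the ordinary reading. That count can favour treatment while other use doubles. With cannabis halved from 46.7 of 70 days, it does so at any control level of other use below about 23 of 70 days. For reductions of 25% and 75% the limit is about 17 and 26 days if the two kinds of use fall on days independently. Above these limits the masking disappears. The figures assume a control group that stays at its entry rate.

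The mismatched baseline covariate is a separate and smaller flaw that does not contribute to the masking.

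Severity is minor. This is a secondary outcome in an 18-subject pilot, other provisions cover part of the question, and any estimate will be imprecise. The gain is a correctly defined, prespecified estimate of substitution.

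**What to change.** In section 8.9:

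1. Define any substance use: whether cannabis, alcohol and nicotine count, and which source supplies the days.
2. Add days of non-cannabis substance use (alcohol and other drugs, from the weekly inventory) as a secondary outcome, adjusted for the same measure at baseline. If the inventory gives only separate counts for alcohol and for other drugs, report the two separately, since their combined days cannot be recovered from the totals.
3. Adjust any-substance days for their own baseline, in line with what 8.9 already does for mood outcomes.
4. Keep any-substance days, labelled as an outcome of total abstinence.

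The inventory is already scheduled at both baseline visits and weekly during treatment, so no new data are needed. The cost is one more exploratory secondary estimate to fit and report, or two if alcohol and other drugs are kept apart.
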